15.4.2. Clinical Laboratory Evaluations

Laboratory parameters will be summarized in standard international (SI) system of units by treatment group using descriptive statistics at Baseline and at each on-study evaluation. Re-test or unscheduled results will not be summarized but will be included in the data listings. The change from Baseline will also be summarized. Baseline is defined as the mean of all available evaluations prior to treatment.

In addition, shift tables (ie, low-normal-high at Baseline versus low-normal-high at post Baseline visit in a 3-by-3 contingency table) from Baseline to worst value, last value, and at each scheduled post-Baseline visit will be provided for hematology and serum chemistry by treatment group to assess changes in laboratory values from Baseline to each on-study evaluation.

Vital Signs and Weight

The results and change from Baseline to each on-study evaluation visit will be summarized by treatment group for weight, oral temperature, sitting heart rate, respiratory rate and sitting blood pressure.

Electrocardiograms

Electrocardiogram (ECG) results will be summarized at each on-study visit descriptively, including the number and percentage of patients with normal, abnormal not clinically significant, and abnormal clinically significant results at Baseline and each on-study evaluation.

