8.4.1. Reasons for Additional Monitoring or Mandatory Interruption of Investigational Product

8.4.1.1. Reasons for Additional Monitoring Related to Liver Chemistries

Patients who develop ALT or AST $>2\times$ baseline (and $>ULN$) or total bilirubin $>1.5\times$ baseline (and $>ULN$) should have repeat testing within 48 to 72 hours to confirm values. Patients with persistent elevations (eg, additional lab testing per Investigator discretion) should be closely monitored. Concomitant elevations in total bilirubin or INR with persistent increases in ALT or AST should also be closely monitored.

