8.4.1.2. Reasons for Investigational Product Interruption Related to Elevated Liver Chemistries

Development of any of the following clinical laboratory values, without explanation, during the study mandates investigational product interruption:

- AST and/or ALT $>3\times$ baseline (and $>ULN$)
- Total bilirubin $>2\times$ baseline (and $>ULN$)

Repeat testing within 48 to 72 hours to confirm the abnormalities and to determine if they are increasing or decreasing should be performed. Detailed adverse event information should also be collected, and the patient should be investigated for possible causes of the liver chemistry changes, as appropriate. The Investigator should obtain a history of concomitant medications (including nonprescription medications and herbal and dietary supplement preparations) and other possible causes of liver enzyme and bilirubin increases. Any potentially hepatotoxic medications should be identified and discontinued if advisable.

If symptoms persist or repeat testing shows AST or ALT $>3\times$ baseline (and $>ULN$) or total bilirubin $>2\times$ baseline (and $>ULN$), patients should be followed as clinically indicated depending on other laboratory and clinical signs and symptoms.

For the purposes of this protocol, if the above referenced significant elevation in liver enzyme or bilirubin levels resolve following interruption of investigational product and no other cause for the elevation is identified, the elevations should be assumed to be related to investigational product and investigational product should be discontinued. If the liver enzyme or bilirubin levels do not resolve following interruption of investigational product and no other cause for the elevation is identified, it may be assumed that the elevations were due to disease progression and the patient may be re-challenged following a discussion between the Investigator or designee and the Sponsor.

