All hepatic injury events, regardless of relationship to investigational product, will be adjudicated by the Hepatic Safety Committee (see [Section 15.9](#)).

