15.4. Safety Analyses

Safety analyses will be conducted using the Safety population. Safety data, including AEs, vital signs, ECG, and clinical laboratory results will be summarized by treatment group using the Safety Population.

The incidence of TEAEs and SAEs will be tabulated by system organ class (SOC) and preferred term for each treatment group, and similarly by severity and relationship to treatment.

Laboratory parameters, physical examinations including vital signs, and ECGs will be summarized by treatment group using descriptive statistics at Baseline and at each scheduled post-Baseline visit. The absolute change from baseline will also be summarized.

CP scores will be summarized by treatment group at Baseline and at each post-Baseline visit.

No inferential comparison with formal statistical hypothesis testing will be performed for safety endpoints.

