15.9. Adjudication Committees

All suspected liver-related clinical events, major adverse cardiovascular events (MACE)/expanded MACE, and drug-related hepatic injury events that occur after administration of the first dose of investigational product will be reviewed by the following blinded adjudication committees, depending on event type, before inclusion in any analysis. The 3 committees and event types they are responsible for adjudicating are as follows:

- Cardiovascular Adjudication Committee (CAC): Adjudicates all suspected MACE, including all deaths

- Hepatic Outcomes Committee: Adjudicates all deaths and suspected liver-related outcomes
- Hepatic Safety Committee: Adjudicates all suspected drug-related hepatic injury events

Each adjudication committee will have a charter that documents the reporting of events by the study site, definition of the suspected events to be adjudicated, supply of source documentation to the committee, entire data flow and process from committee membership, review of the events by the committee, reporting of the final assessment, and the working procedures of the committee.

The adjudication committee members will include experts with relevant adjudication experience; they will not be involved in the study as Investigators, DMC members, or consultants. Any candidate found to have a conflict or whose name is listed on the FDA debarment list is not offered membership. Conflicts of interest are assessed regularly, and if members are found to have a new conflict of interest they will be replaced.

The adjudication of suspected events will be based on available source documentation, including but not limited to individual clinical study data, hospital records, histology, discharge summaries, and/or death certificates. The adjudication committees will not receive any individual patient treatment or site-specific information. The assessment of events will be conducted in compliance with study-specific procedures, manuals, GCP, and all other applicable regulatory requirements, including the archiving of essential documents.

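### Section 15.4.2 excludes re-test and unscheduled laboratory results from summaries yet plans worst-value tables without naming their source, and Sections 8.4.1.2 and 15.9 disagree on which liver injuries are adjudicated

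*Protocol*

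**What the plan says.** Laboratory summaries. Section 15.4 has laboratory parameters "summarized by treatment group using descriptive statistics at Baseline and at each scheduled post-Baseline visit". Section 15.4.2 adds that "Re-test or unscheduled results will not be summarized but will be included in the data listings", and defines baseline as the mean of every evaluation available before treatment. Its next paragraph plans shift tables on a three-by-three low/normal/high grid "from Baseline to worst value, last value, and at each scheduled post-Baseline visit will be provided for hematology and serum chemistry by treatment group". It does not say which results supply the worst and last values.

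Off-schedule liver tests. Under Section 8.4.1.1, patients with ALT or AST above 2 times baseline, or total bilirubin above 1.5 times baseline (each also above ULN), "should have repeat testing within 48 to 72 hours to confirm values". Section 8.4.1.2 sets the interruption thresholds at 3 times baseline for AST/ALT and 2 times for bilirubin, again with ULN, and says: "Repeat testing within 48 to 72 hours to confirm the abnormalities and to determine if they are increasing or decreasing should be performed". It also asks for laboratory follow-up no later than 2 weeks after treatment is resumed. Section 9.7.14 allows unscheduled visits with laboratory tests at any time.

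Adjudication. Section 8.4.1.2 states: "All hepatic injury events, regardless of relationship to investigational product, will be adjudicated by the Hepatic Safety Committee", and refers to Section 15.9. Section 15.9 gives the remit as: "Hepatic Safety Committee: Adjudicates all suspected drug-related hepatic injury events".

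**The concern.** Safety against placebo is a primary objective, clinical laboratory assessments are among its measures (Table 5), and Section 5.5 links hepatotoxicity to liver concentrations of the drug. The protocol orders extra liver tests to confirm a rise and see its direction. An unqualified rule that such tests are never summarised leaves the worst-value table open to two different programs from the same text. Under the literal one, the tables can show a lower maximum than the one observed.

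The grid is a second mismatch. Monitoring is defined in multiples of the patient's own baseline, but the shift tables classify against the reference range. In moderate to severe hepatic impairment, some patients will start above that range.

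The committee's remit is a third and separate conflict. Whether blinded hepatic reviewers see an event should not turn on which section the site follows.

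**Working it through.** The plan gives no figure to reproduce. The check is of the text, with small illustrations on assumed values.

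1. **What feeds the worst value.** Take an assumed ALT course in multiples of baseline, with the trigger at a scheduled visit and then the re-test.
   - Trigger 2.1, re-test 3.5. Scheduled results only: worst = 2.1. All results: max(2.1, 3.5) = 3.5. The patient passes the protocol's own 3-times line only on the second count.
   - Trigger 2.1, re-test 1.5. Worst = 2.1 on both counts. Nothing is lost.
   - Peak seen only at an unscheduled visit. On the literal reading it contributes nothing to any laboratory summary.

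   The loss is therefore confined to re-tests above their trigger and to peaks seen only off schedule. The same ambiguity affects the last value when a patient's final result is unscheduled.

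2. **What the grid can show.** Multiply an assumed baseline (in ULN units) by the rise.
   - Baseline 1.5: 1.5 × 1.0 = 1.5; 1.5 × 2.1 = 3.15; 1.5 × 3.5 = 5.25. All are high, so the cell is high-to-high throughout.
   - Baseline 0.9: 0.9 × 1.0 = 0.9 (normal); 0.9 × 2.1 = 1.89 and 0.9 × 3.5 = 3.15 (both high). The table shows a move, but cannot separate 2.1 times from 3.5 times.

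   Adding re-tests does not change the first patient's cell. The source of the values and the scale are separate defects.

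3. **Adjudication.** Section 8.4.1.2 covers all hepatic injury whatever its relationship to product. Section 15.9, which it cites, covers suspected drug-related injury. An event judged unrelated is in under the first and out under the second. Appendix A shows that the all-events sentence was added in Version 2; the committee's remit line and the re-test sentence are worded the same in both protocol versions.

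4. **Whether visit spacing gives the size.** Table 1 has post-baseline chemistry at Weeks 3, 6, 12, 18, 24, 30, 36 and 48, so the gaps are 3, 3, 6, 6, 6, 6, 6 and 12 weeks (sum 48). For an excursion of assumed length L starting uniformly over 48 weeks, the chance of meeting a scheduled draw is Σ min(L, gap)/48.
   - L = 1 week: 8/48 = 17%.
   - L = 3 weeks: 24/48 = 50%.
   - L = 4 weeks: (3 + 3 + 6 × 4)/48 = 30/48 = 63%.

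   The remainder is not the share lost from the tables. An excursion that meets no scheduled draw and prompts no unscheduled one is never measured, and no table rule can recover it. The calculation also says nothing about re-tests that exceed a scheduled trigger. The lengths are assumptions; the documents give none.

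**The case against.** The strongest reply concerns the shift-table sentence. It opens a new paragraph, and the word scheduled qualifies only its third item, so worst and last value may draw on all results. That stands: the protocol does not expressly bar re-tests from the worst value. The two paragraphs are unreconciled, which is narrower than a stated prohibition.

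A reader might go further and infer that re-tests are kept out of every safety summary, or that the main hepatic-safety tables omit the peaks. The documents do not support this. Abnormal laboratory findings can be adverse events and reach the TEAE and SAE tables. The results stay in the listings, the DMC reviews laboratory data, and a trigger value from a scheduled visit remains in the tables. No table is designated as the primary hepatic-safety table.

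It can also be said that size of change is shown by the change-from-baseline summaries and by the ANCOVA of absolute and percentage change in Section 15.5, and that a multiples-of-baseline table is a matter for the SAP. This stands in part: leaving such a table to the SAP is no fault by itself. But the first are group summaries at visits and the second is a Week 48 analysis. Neither shows a patient's worst value, and the grid the protocol does specify cannot.

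On adjudication, a reader might infer that investigator attribution can remove liver events from the analysis. The documents do not show that. Section 15.9 leaves the definition of suspected events to charters, and the Hepatic Outcomes Committee reviews all deaths and suspected liver-related outcomes without a drug-relationship condition. Nothing takes unadjudicated events out of the adverse-event tables. What remains is the plain contradiction over the Hepatic Safety Committee's remit.

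**Conclusion.** The point holds in a limited form. The exclusion sentence and the worst- and last-value tables need reconciling; on the literal reading, higher re-tests and off-schedule peaks drop out of laboratory summaries only. The low/normal/high grid does not match the protocol's own baseline-multiple thresholds. Sections 8.4.1.2 and 15.9 contradict each other outright, and that needs no assumption.

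No count of affected peaks can be derived. It depends on how long excursions last and how often off-schedule tests are drawn, and the documents give neither. Safety analyses are descriptive, so no test result is at risk. The tables are small, though: with about 50 patients randomised 1:1, each arm has about 25, and one patient in the wrong category moves a proportion by 1/25 = 4 percentage points. That justifies an inexpensive correction and does not call the design into question.

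**What to change.** - **Section 15.4.2, source of values.** Keep by-visit summaries to scheduled results. State that worst and last on-treatment values use all post-baseline results, including re-tests and unscheduled draws. Word the on-treatment window so that a re-test taken just after an interruption is not excluded by definition.
- **Section 15.4.2, scale.** Add a worst-value table by treatment group in multiples of baseline, at the cut-points already in Sections 8.4.1.1 and 8.4.1.2: ALT/AST above 2 and above 3 times, total bilirubin above 1.5 and above 2 times, each with the above-ULN condition. This is for display only and changes no monitoring or interruption rule.
- **Section 15.9.** Reconcile the Hepatic Safety Committee's remit with Section 8.4.1.2 so that adjudication does not depend on attribution, and carry the same definition into the charter.

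The laboratory data are already collected. The cost is protocol and SAP wording, a few extra tables and somewhat more adjudication packets.

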Elevation of liver enzymes or bilirubin is based on comparison to baseline values defined as the mean of all available Screening and Day 1 values, which are the mean of all available evaluations prior to the first administration of investigational product. At least 2 of these samples will be obtained a minimum of 2 weeks apart during the Screening period. Elevations that occur gradually over the course of the study may be indicative of disease progression and should be assessed as clinically appropriate. Liver enzyme and bilirubin elevations that occur over a shorter time, such as within a 6-month period, should be evaluated for drug-induced liver injury as provided in the guidelines below.

If at any time a patient develops signs or symptoms of hepatotoxicity such as new onset fatigue, nausea, vomiting, right upper quadrant pain or tenderness, fever, rash, and/or eosinophilia (>7%) in combination with elevations in liver enzymes, investigational product should be interrupted and liver enzymes monitored until signs or symptoms resolve.

Patients who develop evidence of severe drug-induced liver injury that is suspected to be causally related to the investigational product should be discontinued from investigational product and should not be rechallenged. Severe drug-induced liver injury includes, but is not limited to, functional hepatic impairment, as indicated by rising bilirubin or INR that cannot be explained by progression of disease. Natural progression of the underlying condition and other causal factors such as a common bile duct stone or development of other concurrent liver disease should be considered before the investigational product is permanently discontinued.

If after all investigations and actions outlined above have been completed, the investigator determines that the elevations in liver biochemistries are considered not related to investigational product, the Sponsor must be contacted before investigational product can be reinitiated. Follow-up procedures for patients resuming treatment, including laboratory evaluations and physical examinations, must be performed after a maximum of 2 weeks of retreatment. Results must be reported to the site as soon as possible so the Investigator can determine if it is appropriate for the patient to continue treatment.

The Medical Monitor must be contacted in all cases of persistent liver biochemistry elevations.

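### Section 15.4.2 keeps re-test and unscheduled laboratory results out of summaries with no stated exception for worst values, and its low-normal-high shift scale cannot show a patient already above ULN who crosses the protocol's own liver limits

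*Protocol*

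**What the plan says.** Section 15.4.2 (Protocol Version 2) summarizes laboratory parameters by arm with descriptive statistics at baseline and at each on-study evaluation, and adds: "Re-test or unscheduled results will not be summarized but will be included in the data listings". A new paragraph then provides "shift tables (ie, low-normal-high at Baseline versus low-normal-high at post Baseline visit in a 3-by-3 contingency table"), from baseline to worst value, to last value and to each scheduled post-baseline visit, for hematology and serum chemistry.

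Section 8.4.1 works differently in two respects.

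- **It orders tests off the visit schedule.** At the monitoring limits (ALT or AST above 2x baseline, or total bilirubin above 1.5x baseline, each also above ULN), patients "should have repeat testing within 48 to 72 hours to confirm values" (8.4.1.1). At the interruption limits (ALT or AST above 3x, or bilirubin above 2x, each also above ULN), 8.4.1.2 again asks for "Repeat testing within 48 to 72 hours to confirm the abnormalities". After a restart of drug, laboratory follow-up "must be performed after a maximum of 2 weeks of retreatment". Section 9.7.14 also allows unscheduled visits with extra laboratory tests.
- **It judges rises against the patient's own baseline.** Section 8.4.1.2 states: "Elevation of liver enzymes or bilirubin is based on comparison to baseline values", defined there as the mean of the pre-treatment values.

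**The concern.** Safety and tolerability is one of the two primary objectives (Section 6.1), and Section 5.5 names raised transaminases and bilirubin as a known risk. Formal safety testing is ruled out (Section 15.4), so the descriptive tables by arm carry much of the safety conclusion. The protocol already says which liver rises call for action, yet Section 15.4.2 summarizes on a different scale and by a rule that may discard some of the relevant values. At stake is a by-arm liver summary less sensitive than the collected data would allow.

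**Working it through.** There is no plan figure to reproduce; the check is of reporting rules.

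**1. Do the ordered tests fall on the schedule?** Table 1 (Section 7.1.2) has on-treatment chemistry at Weeks 3, 6, 12, 18, 24, 30, 36 and 48. The gaps from Day 1 are 3, 3, 6, 6, 6, 6, 6 and 12 weeks, then 3 months. Table 1 has no visit for a 48 to 72 hour repeat or for a test within 2 weeks of restarting drug. Such tests will normally fall between scheduled visits and so come under the exclusion sentence as worded.

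**2. Which cells can the exclusion change?** A patient above ULN at baseline whose values stay above it is High-to-High with or without the off-schedule result. A patient at or below ULN at baseline who is High at any scheduled visit already has a High worst value. In the 3-by-3 table the literal rule therefore mainly affects patients not above ULN at baseline whose rise was caught only off schedule. In a table of multiples of baseline it would matter more: 2.5x at a visit and 3.2x on repeat is a crossing of the 3x limit only if the repeat counts.

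**3. What does the scale do with a crossing?** Let b be baseline in units of ULN and m the limit (1.5, 2 or 3). If b > 1 and the post-baseline value exceeds m x b, that value also exceeds 1, so the cell is High-to-High. Values set 1% above the interruption limit, post = 1.01 x m x b, at assumed baselines:

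| Baseline (x ULN) | ALT/AST, m = 3 | Bilirubin, m = 2 | Cell |
|---|---|---|---|
| 0.5 | 1.52 | 1.01 | Normal-to-High |
| 0.8 | 2.42 | 1.62 | Normal-to-High |
| 1.2 | 3.64 | 2.42 | High-to-High |
| 1.5 | 4.54 | 3.03 | High-to-High |
| 2 | 6.06 | 4.04 | High-to-High |
| 3 | 9.09 | 6.06 | High-to-High |

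This holds however worst value is read.

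**4. Do other outputs show it?** Take bilirubin from 4.0 to 8.4 mg/dL (8.4/4.0 = 2.1x), assuming 4.0 is above the laboratory's ULN.

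- Mean change at that visit, 25 per arm (50/2): k crossers add k x 4.4/25, that is 0.18 mg/dL for 1, 0.53 for 3 and 0.88 for 5. The mean moves but does not count patients.
- MELD by the Section 14.1.2 formula, assuming INR 1.5 and creatinine 1.0: 3.78 ln(4.0) + 11.2 ln(1.5) + 9.57 ln(1.0) + 6.43 = 16.21, and with 8.4 in place of 4.0, 19.02. MELD change moves (16 to 19), but both scores fall in the top MELD shift category of 15 or more (Section 15.5). The MELD event in Section 15.6 is open only to patients at 12 or below at baseline.
- Child-Pugh: both values exceed 3.0 mg/dL and score 3 points (Table 10), so the score does not move.

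**5. How many patients could be affected?** The documents give no baseline distribution. For assumed shares above ULN of 30%, 50%, 80% and 100%, 25 x share = 7.5, 12.5, 20 and 25 patients per arm. A substantial share is plausible for bilirubin, which scores in Child-Pugh and at 2x ULN is part of one cirrhosis criterion (Section 8.2). For ALT and AST the documents give nothing.

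**The case against.** The strongest reply is that the exclusion sentence sits in the by-visit descriptive paragraph, and Section 15.4 gives those summaries the scope of scheduled visits. The shift tables open a new paragraph and list worst value apart from scheduled visits, which suggests that worst value may draw on all results. Keeping re-tests out of visit means is ordinary practice. That reading is reasonable, and it is why one cannot say flatly that off-schedule tests reach listings only. But the sentence has no limit on its face, and two programmers could build different worst-value tables from it.

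Second, the ordered repeats mostly confirm a rise already seen. If it was first seen at a scheduled visit, it is already summarized. This stands: the real loss is confined to crossings first seen off schedule, higher peaks on repeat, and rises after restart.

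Third, other by-arm outputs carry part of the signal: Week 48 percentage change, MELD change, and adverse event tables including events leading to withdrawal. The DMC reviews laboratory results by dummy-labelled arm, and "All hepatic injury events, regardless of relationship to investigational product, will be adjudicated by the Hepatic Safety Committee". All true, but these concern means, scores or events; none is specified as a count of patients crossing the numeric limits.

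Fourth, threshold tables are commonly left to the SAP, which is not at hand. Their absence alone would be no finding. The point rests on what the protocol does fix: an unqualified exclusion and a scale that differs from the one it uses to act. For pruritus and fatigue, Section 15.4.3 does define worsening against baseline, with a rule for patients already severe.

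**Conclusion.** The point holds as a modest but worthwhile correction. For the exclusion it is an unresolved ambiguity whose literal reading loses information. For the scale it is certain arithmetic: every crosser who starts above ULN appears as High-to-High. In the extreme case of an arm of 25 all above ULN, 0 and 5 crossers give the same table. How many real patients this touches is unknown, since the 30% to 100% range is assumed.

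Three stronger inferences are not supported:

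- **That a liver signal would be lost.** The listings and the outputs above remain.
- **That the visit gaps give the percentage of rises the rule hides.** Such a figure would depend on assumed onset and duration, would include rises nobody tested, and would not apply to repeats triggered by a scheduled draw.
- **That a numeric crossing equals a mandated interruption.** Section 8.4.1.2 reads "Development of any of the following clinical laboratory values, without explanation, during the study mandates investigational product interruption", so an explained rise does not qualify.

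**What to change.** In Section 15.4.2:

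1. Limit the re-test and unscheduled exclusion to the by-visit descriptive statistics.
2. State that worst-value summaries use all post-baseline results, including re-test and unscheduled ones.
3. Keep the shift tables and add one by-arm table: number and percent of patients whose worst post-baseline value exceeds 2x and 3x baseline for ALT or AST, or 1.5x and 2x baseline for total bilirubin, each also above ULN. Label it as numeric crossings, not mandated interruptions.
4. Beside it, show the number of off-schedule liver tests by arm.

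The cost is a wording change and one table from data already collected. The drawback is uneven ascertainment: patients tested more often have more chances to cross. The test counts make that visible.
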